3.4.3.1. Subgroup Analysis for the Primary Efficacy Endpoint

In addition to the analysis of the overall study population, subgroup analysis will be conducted for the ELFI (primary efficacy endpoint) using linear mixed models to detect significant differences in longitudinal change in ELFI score between treatment groups in the following subgroups: i) palliative-intent treatment subgroup; and ii) adjuvant/curative-intent treatment subgroup.

3.4.3.2. Sensitivity Analyses

Sensitivity analyses will be performed using pattern-mixture models and/or joint model of longitudinal and survival data to help interpret results if greater than 20% of the ELFI data are missing, and if reasons for missing data (from the CoMiDa form) and patterns of missing data suggest that these when data are not missing at random.

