3.6.2. Time Window for Patient-Reported Outcome and Clinical Assessments

It is very important that the PRO assessments are completed within acceptable time limits surrounding the scheduled assessments.

Baseline assessment should be completed at enrolment and must be completed prior to randomisation. The time window for baseline assessment is therefore the time between obtaining consent and treatment allocation.

For the test-retest assessment (week 1), the time window is from 7 days post-baseline assessment to immediately prior to receiving the first dose of chemotherapy.

For the follow-up assessments (week 12, week 18, week 24) and end of study assessment, a time window of up to +/- 3 weeks is allowed

Researcher forms should be completed on the same day as the PRO forms where possible.

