4.3.3. Primary HRQoL Analysis

The primary HRQoL analysis is defined prospectively as a comparison of the longitudinal change in TOI scores for significant between-group difference using linear mixed models. The models will include baseline variables (baseline TOI score, and possibly other baseline variables predictive of TOI outcome) as covariates and treatment arm and time (and their interaction) as fixed effects. Time will include the baseline, 12 week, 18 week and 24 week time-points.

These models account for covariance between repeated measures on participants and will be used to: i) describe the time course of the TOI over time; ii) assess whether the time course differs between the two treatment arms by testing the study arm-by-time interaction; and iii) estimate and test differences between the two treatment arms at specific time points of interest via selected linear contrasts. Sensitivity analyses will be performed using pattern-mixture models and/or joint model of longitudinal and survival data to help interpret results if greater than 20% of the TOI data are missing, and if reasons for missing data (from the CoMiDa form) and patterns of missing data (described in **Section 4.3.2.**) suggest that these when data are not missing at random.

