3.4.2. Missing PRO data

Missing data can be classified by:

- i. Extent of missingness:
 - missing items (one or more missing responses within a questionnaire); or
 - missing forms (the whole questionnaire is missing for a patient)
- ii. Reason for missingness:
 - missing completely at random (MCAR): missing data is independent of all responses (i.e. loss completely by chance); or
 - missing at random (MAR): missing data depends on other observed responses but independent of the value of the unobserved response; or
 - missing not at random (MNAR): missing data depends on the value of the unobserved response

There are two important potential consequences of missing PRO data: (1) decreased precision (wider confidence intervals) and less power to detect statistically significant differences; (2) potential for bias in the estimation of both between (e.g. treatment effect) and within group effects (e.g. change over time).(24) For example, in oncology, patients who are sicker may be less likely to complete HRQOL questionnaires which may potentially overestimate HRQOL and underestimate the adverse effects of cancer and cancer therapy.

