3.4.2.1. Missing HRQOL data patterns

Prior to conducting analyses of HRQOL data, rates and reasons for missing PRO questionnaires will be summarised to assess the extent to which data are missing at random. This is an important first step, as it aids interpretation of the results of HRQOL outcome analyses relative to the assumptions of those analyses.

A table of HRQOL completion rates by arm will be reported. Following NCIC Clinical Trials Group (NCIC CTG) recommendations(25), completion rates at each follow-up timepoint will be calculated in two ways, that is, HRQOL assessments completed as a percentage of: 1) all participants recruited (i.e. number of baseline HRQOL completions); 2) number of HRQOL assessment expected (i.e. number of participants still alive and on-study at that timepoint).

Table 2. Rate and reasons for missing ELFI data

Status/Reason	All Study Participants (N=)			
	Week 0	Week 12	Week 18	Week 24
	N (%)	N (%)	N (%)	N (%)
Completed				
Patient refused				
Patient feels too ill				
Staff felt patient too ill				
Staff oversight				
Other, not specified				

Unknown				
Patient death				
% of surviving patients				
% of total patients				

Table 3. Rate and reasons for missing ELFI data, according to treatment groups

Status/Reason	Intervention Group (N=)				Usual Care Group (N=X)			
	Week 0 N (%)	Week 12 N (%)	Week 18 N (%)	Week 24 N (%)	Week 0 N (%)	Week 12 N (%)	Week 18 N (%)	Week 24 N (%)
Completed								
Patient refused								
Patient feels too ill								
Staff felt patient too ill								
Staff oversight								
Other, not specified								
Unknown								
Patient died								
% of surviving patients								
% of total patients								

To explore mechanisms of missingness, a graph of the ELFI versus time will be graphed, stratified by dropout time.(24) If the trajectories over time are substantially different, this will suggest data are not missing completely at random. For example, if participants who have lower baseline values are more likely to drop out, or if steeper rates of decrease in ELFI over time are associated with earlier dropout, missing data are more likely to be linked with sicker participants. We will also use these graphs to assess whether the separation between the missingness patterns is more dramatic in the intervention arm than the control arm.

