3.4.3. Primary HRQOL Analysis

The primary HRQOL analysis is defined prospectively as a comparison of the longitudinal change in ELFI scores for significant between-group difference using linear mixed models. The models will include baseline variables (baseline ELFI score, and possibly other baseline variables predictive of ELFI outcome) as covariates and treatment arm and time (and their interaction) as fixed effects. Time will include the baseline, 12 week, 18 week and 24 week assessment points. Time is continuous in linear mixed model.

These models account for covariance between repeated measures on participants and will be used to: i) describe the time course of the ELFI over time; ii) assess whether the time course differs between the two treatment arms by testing the study arm-by-time interaction; and iii) estimate and test differences between the two treatment arms at specific time points of interest via selected linear contrasts.

Linear mixed models account for missing data by using information from the observed data to implicitly impute unobserved data.

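### The missing-not-at-random sensitivity analyses depend on a two-part trigger: one part cannot be settled from observed data, the other has no stated denominator, and the overview sections attach no trigger at all

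*Combined protocol and SAP*

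**What the plan says.** The primary analysis (SAP 3.4.3) is a linear mixed model for ELFI, the protocol's TOI under a new name. On its time axis: "Time will include the baseline, 12 week, 18 week and 24 week assessment points". Missing scores are handled implicitly, through what the model borrows from observed scores.

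SAP 3.4.3.2 adds pattern-mixture and/or joint longitudinal-survival models, but only "if greater than 20% of the ELFI data are missing, and if reasons for missing data (from the CoMiDa form) and patterns" suggest that the data are not missing at random. Protocol 4.3.3 has the same rule: "if greater than 20% of the TOI data are missing, and if reasons for missing data (from the CoMiDa form) and patterns". The synopsis also joins the two conditions with an 'and'. The overviews in SAP 3.4.1 and protocol 4.3.1 name the same models as sensitivity analyses and attach no condition.

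On mechanism, SAP 3.4.2 gives the definition "missing not at random (MNAR): missing data depends on the value of the unobserved response" and warns that in oncology "patients who are sicker may be less likely to complete HRQOL questionnaires". SAP 3.4.2.1 plans completion rates by arm at each follow-up visit with two denominators (all recruited; alive and on study), tables of reasons overall and by arm, and a graph of ELFI by dropout time. Of that graph it says: "If the trajectories over time are substantially different, this will suggest data are not missing completely at random".

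**The concern.** The primary result assumes that, given the observed scores, missing scores follow the model. The SAP itself gives a reason to doubt this: sicker patients may return fewer questionnaires. The pattern-mixture and joint models are the only planned analyses that relax the assumption, and both conditions must hold before they are run.

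The second condition asks the observed data to reveal something defined by unobserved data. The first asks whether a percentage exceeds 20% without saying what it is a percentage of. With the and/or between models also open, whether and how robustness is tested would be decided after the data are seen, in an open-label trial with a self-reported endpoint. A treatment difference, or the lack of one, could then be reported with no analysis showing how far it depends on the missing scores.

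**Working it through.** **1. The design yardstick.** SAP 3.2.1 gives a two-sided 0.05 level, 80% power, effect size 0.5 and 64 evaluable per group. The two-sample t-test needs 63.77, so 64 per group, with power 80.1%. The plan's figure reproduces, and 0.5 SD is the scale used in step 4.

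**2. The second condition.** Three sources could inform it.
- *The definition.* Under SAP 3.4.2, "missing data depends on the value of the unobserved response" in the not-at-random case. The observed scores do not contain that value.
- *The graph by dropout time.* By the SAP's own account, diverging trajectories speak against missing completely at random. They also diverge under missing at random, when dropout follows earlier observed scores. The graph cannot separate missing at random from not at random.
- *The CoMiDa reasons.* An entry such as 'too ill' is relevant but indirect, and no rule says how many such entries, or which, meet the condition.

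A simulation shows the point. With 29% missing, only the unobserved values were lowered by 0, 0.25 and 0.5 SD. The observed mean was 0.146 in all three cases, while the true mean moved by 0, -0.07 and -0.15 SD.

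**3. The first condition.** Four assessment points enter the model. Baseline is taken as complete, because protocol 3.6.2 says: "Baseline assessment should be completed at enrolment and must be completed prior to randomisation". The documents give no dropout rate, so the rates below are assumptions. Pooled rate = sum of visit rates divided by number of visits. For the third row, (0+15+22+30)/4 = 16.75% and (15+22+30)/3 = 22.3%.

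| Assumed missing at baseline / wk 12 / 18 / 24 | Pooled, 4 visits | Pooled, 3 follow-ups | Visits above 20% |
|---|---|---|---|
| 0 / 5 / 10 / 30% | 11.3% | 15.0% | wk 24 |
| 0 / 10 / 20 / 30% | 15.0% | 20.0% | wk 24 |
| 0 / 15 / 22 / 30% | 16.8% | 22.3% | wk 18, 24 |
| 0 / 20 / 25 / 30% | 18.8% | 25.0% | wk 18, 24 |
| 0 / 30 / 30 / 30% | 22.5% | 30.0% | wk 12, 18, 24 |

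The rule needs more than 20%, so in the second row neither pooled rate fires it. In the third row the answer depends on the reading. Deaths matter too: if 15 of the 30 points at week 24 are deaths, missingness among survivors is 15/85 = 17.6% (below); if 10 are deaths, it is 20/90 = 22.2% (above).

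**4. Size at stake.** Let d be how far the missing scores lie from the mixed model's prediction, in SD, and m the fraction missing.
- Departure in one arm only: shift = d × m. For d = 0.5, this is 0.5 × 0.15 = 0.075 SD at 15% missing and 0.5 × 0.30 = 0.15 SD at 30%. Against 0.5 SD these are 15% and 30% of the design effect.
- Same departure in both arms: shift = d × (difference in m). With 25% and 35% missing, 0.5 × 0.10 = 0.05 SD. With equal missingness it is 0.

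The SAP treats time as continuous, so d × m only approximates the shift in a contrast at one visit.

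**The case against.** The plan takes missing data seriously. It records reasons on a dedicated form, tabulates them by arm and visit, graphs trajectories by dropout time, and offers an assessment at early discontinuation expressly to gauge bias from later missing data (protocol 3.6.5.5). The SAP says only that reasons and patterns may suggest a mechanism, which is a fair use of indirect evidence. The mixed model uses baseline and earlier scores, so only the residual departure from its prediction biases the result. All of this stands. But these are diagnostics: none estimates the treatment difference under a different assumption about the missing scores.

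Four stronger readings are tempting, and the documents do not support them.
- A reader might infer that the rule stays silent with 30% missing at week 24, or that average follow-up missingness must exceed 26.7% (20% × 4/3) before it fires. Both presuppose a rate pooled over four visits including baseline. The only completion rates that the SAP defines are per follow-up visit, and on that basis 30% at week 24 meets the first condition.
- A reader might infer that differences between arms are ignored. SAP 3.4.2.1 tabulates missingness by arm and uses the graphs to compare the arms; only the 20% count is not said to be by arm.
- A reader might infer that the plan firmly makes these analyses conditional. The two overviews state them without condition, so the documents disagree.
- A reader might set a bias in points against the 10-unit deterioration in SAP 3.4.4. That is a threshold for an individual's change, and the documents give no ELFI standard deviation for the conversion. The 0.5 SD design effect is the proper comparison.

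**Conclusion.** The concern holds in a limited form. The second condition cannot be settled from observed data and has no decision criterion, so it can block the analyses at any level of missingness and under any denominator. The first condition could be judged once its denominator is fixed; at present, plausible readings give opposite answers on the same data. The overviews contradict the conditional text.

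The possible effect on the primary contrast is moderate: about 0.075 to 0.15 SD for a 0.5 SD departure in one arm with 15 to 30% missing, and nothing where departures and missingness are equal in both arms. Those rates and that departure are assumptions. The defect in the trigger does not depend on them. This does not show that the primary result will be biased; it shows that the plan does not guarantee an analysis that would reveal how sensitive the result is.

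**What to change.** Delete both conditions in SAP 3.4.3.2, protocol 4.3.3 and the synopsis, so that they agree with SAP 3.4.1 and protocol 4.3.1. Always run one prespecified missing-not-at-random analysis of ELFI, whatever the observed rate or pattern. One example is a delta-adjusted pattern-mixture model, with the shift varied separately by arm over a range stated in advance. Apply it to the week-12 contrast, on which the sample size rests, and to the later contrasts. Settle the and/or before the data are examined (the joint model can be optional), and state how scores after death are handled.

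Completion rates by arm are already planned and need no change. No new data are required; the cost is a little more analysis work.

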3.4.4. Secondary HRQOL Analyses

Secondary HRQOL analyses, defined prospectively, includes: i) comparison of the proportions of participants in the two treatment arms with at least 10 units deterioration in ELFI score at 12 weeks, 18 weeks and 24 weeks by using Fisher's exact test (as recommended by NCIC CTG)(25); and ii) time to deterioration in ELFI score (defined as the time from randomisation to a minimum 10 units deterioration in change score from baseline) by log-rank test.

3.4.5. Tertiary HRQOL Analyses

Tertiary HRQOL analyses will be performed on all scales of the EORTC QLQ-C30, QLQ-ELD14 and EQ-5D-5L to complement primary and secondary HRQOL analyses, to make full use of all HRQOL data collected, and to assist in interpretation of the primary endpoint. The t-test or Wilcoxon test will be applied, depending on normality of distribution, to each of the scales of the QLQ-C30 and QLQ-ELD14 (using the EORTC's standard scoring algorithms) and the EQ-5D-5L, to assess between-group differences in change from baseline to 12 weeks, 18 weeks and 24 weeks, across a comprehensive range of HRQOL domains. The ELFI will also be analysed in this way for completeness.

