3.2. Sample size

3.2.1. Sample size required

Based on reviews of published studies, a minimal important difference in patient-reported outcome scores has commonly been set at approximately half the standard deviation; that is, equivalent to an effect size of 0.50.(20, 21) An effect size of 0.5 is commonly regarded as a medium difference and a meta-analysis has shown it to be clinically relevant in studies of quality of life using QLQ-C30 as an outcome measure.(22, 23)

The target sample for this study was based on an independent t-test at a 2-sided significance level of 0.05 to have an 80% power to detect a significant between-group difference in ELFI from baseline to 12 weeks with an effect size of 0.5. Under these assumptions, the minimum sample size is 64 evaluable participants in each group (or a total of approximately 128 evaluable participants) who have completed the primary outcome measure at two separate timepoints.

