3.5.2. Other Secondary Endpoints

Other secondary endpoints will be summarised according to established guidelines specific to the measurement instrument. In general, categorical variables will be tabulated and key summary statistics (mean, standard deviation, median, range, etc.) will be presented for continuous measurements. Comparisons between treatment arms will be made where appropriate and the test selected depending on the distribution.

Secondary endpoints were specified in the protocol as follows:

- Performance Status The mean self-rated ECOG score and KPS score of patients at 12 weeks and 24 weeks are secondary endpoints; they will be compared between treatment arms.
- Functional Status The proportion of participants in each treatment arm with functional decline in the ADL and/or IADL scores at 12 weeks and 24 weeks are secondary endpoints of this study; they will be compared between treatment arms.
- Mood The proportion of participants in each of the PHQ-9 and GAD-7 categories (cut-points 5, 10 and 15) in the two treatment arms at 12 weeks and 24 weeks are secondary endpoints of this study; they will be compared between treatment arms.
- Nutrition The proportion of participants with self-MNA score ≤ 11 points and >11 points in the two treatment arms at 12 weeks and 24 weeks is a secondary endpoint of this study and will be compared between treatment arms.
- Health Utility The EQ-5D-5L health utility score in the two treatment arms at 12 weeks and 24 weeks are secondary endpoints of this study and will be compared between treatment arms.
- Chemotherapy delivery Secondary endpoints of this study are the mean RDI of chemotherapy, the proportion of participants with dose reduction $\geq 10\%$ from previous dose; they will be compared between treatment arms.
- Healthcare utilisation Secondary endpoints of this study are the mean number of: emergency department visits, hospital admissions (including length of hospital stay; and divided into planned and unplanned), medical consultations and type of PBS-listed medications in the two treatment arms from randomisation to 12 weeks and 24 weeks post-randomisation; they will be compared between treatment arms. An additional secondary endpoint is the hazard ratio for hospitalisation of participants in the two treatment arms; this will be compared between treatment arms.

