- Institutionalisation A secondary endpoint of this study is the hazard ratio of institutionalisation of participants in the two treatment arms; this will be compared between treatment arms. In addition, the level of care level of care and social situation will also be described in the treatment arms.

The following endpoint definition was changed from the protocol:

- Chemotherapy delivery: the proportion of participants with dose delays in the two treatment arms at 12 weeks and 24 weeks. Dose delay is defined as a delay of more than 3 days in the start of chemotherapy measured since the start of the previous cycle.

The following endpoints were not defined in the protocol, but will be analysed as exploratory endpoints to supplement the pre-specified secondary endpoints:

- QLU-C10D health utility
- QLU-C10D health utility score in the two treatment arms at 12 weeks and 24 weeks will be compared between treatment arms.(27, 28)
- The QLU-C10D health utility scores will also be used in the health economic analysis, in place of the EQ-5D-5L scores, to determine if the same or different conclusions would be reached with either utility measure.
- Chemotherapy delivery
- Primary dose reduction (PDR) will be compared within treatment arms. PDR is defined as dose of chemotherapy which is less than the dose recommended for given regimen in current treatment guidelines by NCCN (excluding round-off).
- Mean % dose reduction at outset will be compared within treatment arms.
- Median % dose reduction at outset will be compared within treatment arms.
- Early discontinuation of chemotherapy will be compared within treatment arms.
- Mean cycles of chemotherapy delivered will be compared within treatment arms.
- Median cycles of chemotherapy delivered will be compared within treatment arms.

Table 4. Summary of secondary and additional exploratory endpoints, data type, data timepoints and statistical tests are listed in the table below.

Endpoints	Data Type	Data output	Data Timepoints	Statistical Tests
Function				
ECOG-PS	Categorical ordinal (0,1,2,3,4)	contingency table	Baseline Wk12 Wk24	contingency table analysis
KPS	Categorical ordinal (30,40,50,60,70,80,90,100)	contingency table	Baseline Wk12 Wk24	contingency table analysis
Katz ADL scale	6-item, categorical dichotomous scale (i) → dichotomous outcome (unimpaired, impaired) (ii) → dichotomous outcome (any decrease in ADL)	1. unimpaired vs impaired 2. decrease in ADL	Baseline Wk12 Wk24	contingency table analysis

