OARS IADL	7-item, 3-point Likert scale (i) → categorical dichotomous (unimpaired, impaired) (ii) → categorical dichotomous (any decrease in IADL)	1. unimpaired vs impaired 2. decrease in IADL	Baseline Wk12 Wk24	contingency table analysis
Mood				
PHQ9 (depression)	9-item, 4-point Likert scale → categorical ordinal (none, mild, moderate, severe) → categorical dichotomous (not depressed, depressed)	contingency table	Baseline Wk12 Wk24	contingency table analysis
GAD7 (anxiety)	9-item, 4-point Likert scale → categorical ordinal (none, mild, moderate, severe) → categorical dichotomous (not anxious, anxious)	contingency table	Baseline Wk12 Wk24	contingency table analysis
Nutrition				
Self-MNA	6-item questionnaire → categorical dichotomous (malnourished/at risk vs normal) → categorical ordinal (malnourished, at-risk, normal)	1. malnourished/at risk vs normal 2. malnourished vs at-risk vs normal 3. decrease in self-MNA	Baseline Wk12 Wk24	contingency table analysis
Health Utilities				
EQ-5D-5L	5-item, 5-point Likert scale, weighted with Australian utility weights	mean utility weight	Baseline Wk12 Wk18 Wk24	t-test (parametric); or Mann-Whitney test (non-parametric)
QLU-C10D	10-dimensions derived from 13 items of the QLQ-C30, each dimension weighted with Australian utility weights	mean utility weight	Baseline Wk12 Wk18 Wk24	t-test (parametric); or Mann-Whitney test (non-parametric)
Chemotherapy Delivery				
Initial dose (i.e. primary dose reduction)	Categorical dichotomous (full dose, reduced dose)	full dose vs reduced dose	Baseline	contingency table analysis
Mean % dose reduction at outset where applicable	Numerical	mean	Baseline	t-test (parametric); or Mann-Whitney test (non-parametric)
Median % dose reduction at outset where applicable	Numerical	median	Baseline	Mann-Whitney test (non-parametric)
Subsequent dose reduction ≥10%	Categorical dichotomous (yes, no)	yes vs no		contingency table analysis
Subsequent dose escalation	Categorical dichotomous (yes, no)	yes vs no		contingency table analysis
Dose delay >3 days	Categorical dichotomous (yes, no)	yes vs no		contingency table analysis

Early discontinuation	Categorical dichotomous (yes, no)	yes vs no		contingency table analysis
Mean Relative Dose Intensity (RDI)	Numerical	mean		t-test (parametric); or Mann-Whitney test (non-parametric)
Mean cycles delivered	Numerical	mean		t-test (parametric); or Mann-Whitney test (non-parametric)
Median cycles delivered	Numerical	Median		Mann-Whitney test (non-parametric)

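### Tertiary and secondary patient-reported scores are tested visit by visit without adjustment for the collected baseline, week 18 is listed for scales not collected then, and the ECOG/KPS endpoint does not match its test

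*Combined protocol and SAP*

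**What the plan says.** **Tertiary scales.** SAP 3.4.5 states "The t-test or Wilcoxon test will be applied, depending on normality of distribution, to each of the scales" of the QLQ-C30, QLQ-ELD14 and EQ-5D-5L. The outcome is "change from baseline to 12 weeks, 18 weeks and 24 weeks, across a comprehensive range of HRQOL domains". Protocol 4.3.5 plans the same tests at weeks 12 and 24 only.

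**Utilities.** SAP Table 4 (section 3.5.2) lists mean utility for EQ-5D-5L and QLU-C10D at baseline and weeks 12, 18 and 24, with "t-test (parametric); or Mann-Whitney test (non-parametric"). The SAP text above the table compares both instruments at weeks 12 and 24.

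**Missing forms.** The table in SAP 3.4.2.3 gives item-level rules for the secondary instruments and states that no missing form is imputed. For QLQ scales, SAP 3.4.2.2 gives a rule for missing items only. The mixed model with baseline as covariate (SAP 3.4.3) is specified for ELFI alone.

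**Schedule.** SAP 2.5.1 and Protocol 3.6.1 both show the full QLQ-C30 and QLQ-ELD14 at baseline and weeks 12 and 24. At week 18 participants complete the ELFI (TOI) items, EQ-5D-5L and the Global Rating of Change.

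**ECOG and KPS.** SAP 3.5.2 says "The mean self-rated ECOG score and KPS score of patients at 12 weeks and 24 weeks are secondary endpoints". Table 4 classes KPS as "Categorical ordinal (30,40,50,60,70,80,90,100") and ECOG as ordinal with five levels, and assigns both a contingency-table analysis of no stated type.

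**The concern.** These analyses are meant to help explain the ELFI result, and they are specified less well than the ELFI analysis in three respects.

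1. A baseline score exists for every scale, and adjusting for it costs nothing in data. Leaving it out gives away precision. Dropping participants visit by visit also needs a stronger missing-data assumption than a repeated-measures model does. SAP 3.4.2 itself warns that sicker patients may be less likely to return questionnaires.
2. Some planned week-18 tests have no data behind them. One of these, QLU-C10D, matters further because SAP 3.5.2 substitutes QLU-C10D for EQ-5D-5L in the economic analysis to see whether the conclusion changes.
3. For ECOG and KPS the endpoint and the test disagree, and the test is not named. The analyst could choose after seeing the data.

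**Working it through.** **1. The plan's own figure.** SAP 3.2.1 is "based on an independent t-test at a 2-sided significance level of 0.05 to have an 80% power" for a "between-group difference in ELFI from baseline to 12 weeks with an effect size of 0.5", giving 64 per group. The normal approximation gives 63. The exact noncentral t gives power 0.795 at 63 and 0.801 at 64. The stated 64 reproduces and is not in question.

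**2. Week 18: what can be scored.**
- Scales, from Protocol 1.2.2: QLQ-C30 has 5 functional + 3 symptom + 6 single-item + 1 global = 15. QLQ-ELD14 has 5 multi-item + 2 single-item = 7. Total 22.
- The 12 ELFI items form PF2 (5 items), RF2 (2), SF (2) and MO (3). Only these 4 scales can be scored at week 18, and 22 − 4 = 18 cannot.
- QLU-C10D needs 13 QLQ-C30 items (Table 4). The week-18 form carries 5 + 2 + 2 = 9 QLQ-C30 items, so QLU-C10D cannot be computed.
- Cross-check on form length: Global Rating 1 + EQ-5D-5L 6 + TOI 12 = 19 items. At 10 seconds each (Protocol 3.6.4) this is 190 s, or 3.2 minutes, against about 3 minutes stated in Protocol 3.6.5.4. Both full QLQ forms in place of the TOI would make 1 + 6 + 44 = 51 items, or 8.5 minutes. The empty week-18 cell is therefore not a table slip.

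**3. Baseline adjustment.** The documents give no baseline-to-visit correlation r, so a range is assumed, with equal variance at both visits. Relative variances are 1 for the visit mean, 2(1 − r) for the change score and 1 − r² for the baseline-adjusted score. The cut against change is 1 − (1 − r²)/[2(1 − r)] = (1 − r)/2. The cut against the visit mean is r².

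| r (assumed) | Cut vs change | Cut vs visit mean | Adjusted power, 0.5 SD of change | Adjusted power, 0.5 SD of score |
|---|---|---|---|---|
| 0.3 | 35% | 9% | 0.94 | 0.84 |
| 0.5 | 25% | 25% | 0.90 | 0.90 |
| 0.7 | 15% | 49% | 0.87 | 0.98 |
| 0.8 | 10% | 64% | 0.85 | 1.00 |

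The power columns use 64 per arm and a normal approximation; the unadjusted comparator is 0.81 on that basis (0.80 by exact t). The 0.5 SD effect is borrowed from the ELFI calculation for illustration. The SAP states no effect size for these scales.

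**4. Visit-wise complete cases.** No missing rate is given. If 10%, 20% or 30% of 64 per arm lacked the form, 58, 51 or 45 would remain, with exact t power of 0.76, 0.71 or 0.65 at 0.5 SD. A mixed model recovers only part of this: it uses the other visits of a participant who misses one, but gains nothing from a participant with no follow-up at all.

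**5. ECOG and KPS.** With two arms, an unordered table has 5 − 1 = 4 df for ECOG and 8 − 1 = 7 df for KPS, if all levels are populated. The noncentrality giving a 1-df test 80% power is (1.960 + 0.842)² = 7.85. At that value, power is 0.595 on 4 df and 0.493 on 7 df. A simulation with five levels (assumed 20/40/25/10/5%, odds ratio 2.5, 64 per arm) agrees in direction: chi-square 0.58, Wilcoxon 0.81.

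**The case against.** A reader might go further than the documents allow in four ways.

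- *That the tests ignore baseline.* They do not. SAP 3.4.5 tests change from baseline, and ADL/IADL decline, decrease in self-MNA and 10-unit ELFI deterioration all use baseline. What is missing is covariate adjustment. A t-test on change is valid in a randomised trial, and at high correlation little is lost against it (10% of variance at r = 0.8).
- *That the SAP prescribes an unordered test.* It does not. Table 4 itself labels ECOG and KPS ordinal, and a trend test would fit the words used. The fault is that no test is named. The 60% and 49% figures show what the poorest choice would cost, not what is planned.
- *That QALYs will be built on four visits for EQ-5D-5L and three for QLU-C10D.* Neither Protocol 4.5.1 nor SAP 3.5.2 says which visits enter the QALY. The mismatch is a risk to close off, not a stated plan.
- *That week 18 biases a result.* Where no data exist, no test can be run. ELFI, its four component scales and EQ-5D-5L do have week-18 data.

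It is also fair to say that these analyses are supportive, carry no multiplicity control (SAP 3.4.6), and that Protocol 4.3.5 already has the right visits for the QLQ scales. SAP 3.1 mentions logistic regression to adjust for group differences, but it ties this to no endpoint and does not list baseline scores. All of this limits the weight of the point. It does not remove the visit error, the endpoint-test conflict or the avoidable loss of precision.

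**Conclusion.** The point holds in three parts.

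- **Week 18** is a documentary error that needs no assumption: 18 of 22 QLQ scales and QLU-C10D are listed for a visit at which they cannot be scored.
- **ECOG/KPS** is an internal conflict: a mean-score endpoint is paired with an unnamed test for categories.
- **Adjustment and missing forms** is a matter of efficiency and assumptions. The variance saving is 35% to 10% against change scores and 9% to 64% against visit means over assumed correlations of 0.3 to 0.8. The direction is certain in large samples, but the size depends on a correlation the documents do not give. The missing-data effect depends on a rate they do not give either.

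The change is worth making before analysis. It alters neither the primary ELFI analysis nor the sample size.

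**What to change.** (a) Analyse QLQ-C30, QLQ-ELD14, EQ-5D-5L and QLU-C10D scores with a mixed model on follow-up visits only, with arm, categorical visit, arm-by-visit and the scale's own baseline as covariate. The ELFI model in SAP 3.4.3 should not be copied: it includes baseline both as a covariate and as a level of time, and treats time as continuous.

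(b) State one endpoint for ECOG and KPS and match the test to it: either a baseline-adjusted comparison of mean scores or a named ordinal method adjusted for baseline. Keep the protocol-defined proportions for PHQ-9, GAD-7 and self-MNA, and add an ordinal model there only as a supplement.

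(c) Limit week 18 in SAP 3.4.5 to ELFI, PF2, RF2, SF, MO and EQ-5D-5L, and delete week 18 for QLU-C10D in Table 4. When the EQ-5D-5L and QLU-C10D QALYs are compared, compute both on weeks 0, 12 and 24.

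The cost is text and table edits in the SAP, modest programming, and a proportional-odds assumption wherever that model is used. Item (c) sets aside the week-18 EQ-5D-5L value for the head-to-head QALY comparison only. No new data are needed.
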